## 1.0 Introduction

### 1.1 Device Name (working name)

Rapid SARS-CoV-2 Antigen Test (MP Biomedicals, LLC [name]).

### 1.2 Intended Use

The Rapid SARS-CoV-2 Antigen Test is an immunochromatography based one step in vitro test. It is designed for the rapid qualitative determination of SARS-CoV-2 virus antigen in anterior nasal swabs from symptomatic and asymptomatic individuals. The Rapid SARS-CoV-2 Antigen Test Card shall not be used as the sole basis to diagnose or exclude SARS-CoV-2 infection.

### 1.3 Background

Coronavirus disease (COVID-19) is a disease caused by a newly discovered coronavirus, severe acute respiratory syndrome coronavirus 2 (SARS-CoV-2). The SARS-CoV-2 is a  $\beta$ -coronavirus, which is enveloped non-segmented positive-sense RNA virus . It is spread by human-to-human transmission via droplets or direct contact, and infection has been estimated to have mean incubation period of 6.4 days and a basic reproduction number of 2.24–3.58. Among patients with pneumonia caused by SARS-CoV-2, fever was the most common symptom, followed by cough. On 11 March 2020, the COVID-19 outbreak was characterized as a pandemic by the WHO. Since then, over 70 million people worldwide have been infected with the virus with over 1.5 million deaths attributed to the virus. Laboratory testing for SARS-CoV-2 is currently being performed to determine if an individual has active infection via detection of viral RNA or if an individual has an immune response to the virus from a previous infection via detection of antibodies.

Specimen collection is a crucial first step in the evaluation of an individual's SARS-CoV-2 infection status. The goal of this project is to evaluate human usability of a rapid SARS-CoV-2 antigen test for over the counter (OTC) use. Study subjects under EDP supervision, either in-person or via video conference, will collect and test anterior nasal swab samples. The Rapid SARS-CoV-2 Antigen Test collection and testing methodology is viewed as a convenient and inexpensive method to test clinical specimens for SARS-CoV-2 and OTC access will improve the availability of COVID-19 testing.

### 1.4 Principles of the Device

The COVID-19 Antigen Rapid Test Device detects SARS-CoV-2 viral antigens through visual interpretation of color development. Anti-SARS-CoV-2 antibodies

are immobilized on the test region of the nitrocellulose membrane. Anti-SARS-CoV-2 antibodies conjugated to colored particles are immobilized on the conjugated pad. A sample is added to the extraction buffer which is optimized to release the SARS-CoV-2 antigens from specimen. During testing, the extracted antigens bind to anti-SARS-CoV-2 antibodies conjugated to colored particles. As the specimen migrates along the strip by capillary action and interacts with reagents on the membrane, the complex will be captured by the anti-SARS-CoV-2 antibodies at the test region. Excess colored particles are captured at the internal control zone. The presence of a colored band in the test region indicates a positive result for the SARS-CoV-2 viral antigens, while its absence indicates a negative result. A colored band at the control region serves as a procedural control, indicating that the proper volume of specimen has been added and membrane wicking is working. (See Appendix 1).

## **2.0 Scientific Objectives**

### **2.1 Study Rationale**

Traditional specimen collection techniques used in conjunction with respiratory infectious agent identification, for examples nasopharyngeal (NP) swabbing or aspiration, are often uncomfortable for the patient. Anterior nasal (AN) swab samples have provided a more comfortable sampling alternative to NP swabs that is also less technically challenging. With ease of use and convenience for OTC home specimen collection with the Rapid SARS-CoV-2 Antigen Test, the patient experience may lead to better patient sampling for SARS-CoV-2 testing.

### **2.2 Study Objectives**

The objective of the study is to evaluate the usability of the Rapid SARS-CoV-2 Antigen Test in a home setting. The main focus will be to assess the clarity and robustness of the instructions for use.

## **3.0 Study Materials**

EDP Biotech Corp. will obtain the Rapid SARS-CoV-2 Antigen Test kits and materials to perform the collection and testing from the respective manufacturers. EDP Biotech Corp. will maintain proper storage conditions of all reagents per the manufacturers' product package inserts.

### **3.1 Specimen Collection Materials/Equipment**

All Rapid SARS-CoV-2 Antigen Test materials are ready for use as per Manufacturer's instructions. The materials will be used prior to expiration dating.

**Table 1 Rapid SARS-CoV-2 Antigen Test Materials**

Material	Manufacturer	Catalog Number	Storage
Rapid SARS-CoV-2 Antigen Test Card (sealed foil pouch)	MP Biomedicals Solon, OH USA		Ambient (15-25°C)
Sterile swab	Goodwood Medical Care Ltd. [name]		Ambient (15-25°C)
Extraction tube	MP Biomedicals Solon, OH USA		Ambient (15-25°C)
Extraction solution bottle	MP Biomedicals Solon, OH USA		Ambient (15-25°C)
Instructions for use (IFU)	MP Biomedicals Solon, OH USA		Ambient (15-25°C)
Tube stand	MP Biomedicals Solon, OH USA		Ambient (15-25°C)

### 3.2 Computer Hardware and Software

For this study, results will be analyzed using:

- PC Computer Platform.
- Microsoft Office Excel, version 2003 (or higher).

### 3.3 Collection/Storage/Transfer of Data Files

All data will be collected and stored by EDP Biotech Corp. using its established laboratory information systems (LIS) upon completion of the initial testing or resolution of incomplete or disqualified runs. Results will be compiled as a specimen log as part of the clinical study documentation.

If applicable, all original instrument data printouts will be maintained as part of the study records. Additionally, records of personnel performing all assays, all instruments, reagent and control lots used for each assay run will be maintained.

Note: All required ancillary equipment and materials for the study are specified in appropriate Standard Operating Procedures (SOPs), along with the instrument operator's manuals and reagent instructions for use (package insert) at EDP Biotech Corp.

## 4.0 Study Design

This is a clinical study to evaluate the feasibility of using anterior nasal (AN) swabs on Rapid SARS-CoV-2 Antigen Test kits for OTC use in symptomatic and asymptomatic individuals following recommendations from the FDA's July 29, 2020 Template for Manufacturers of Molecular and Antigen Diagnostic COVID-19 Tests for Non-Laboratory Use, Section J 7. EDP Biotech Corp. will recruit subjects for an at home human usability study through the internet as well as by referral throughout the United States. Rapid SARS-CoV-2 Antigen Test specimen collection and testing will be done under the supervision of EDP Biotech Corp. either in person or via video conference. Testing will be observed by EDP Biotech Corp. medical professionals or designees either in person or via video conference. The study subjects shall perform the entire workflow including sample collection, testing, and results interpretation. Following results interpretation, subjects will complete a usability and ease of use questionnaires. The data collected in study may be submitted as a regulatory filing to the US FDA or other agencies. All specimens will be collected from participating consenting subjects. Additional testing of the specimens for research purposes may be performed. The study acceptance criteria is a 95% success rate for subjects producing the control line on the Rapid SARS-CoV-2 Antigen Test and a SUS average score of 68 or greater.

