### 4.3 Specimen Collection

Each potential subject will be asked to complete a form describing any symptoms of respiratory illness being experienced, education level, and basic demographics (Appendices 2 and 3). Subjects will be observed by EDP Biotech Corp. personnel or

designees during sample collection, testing, and shipment preparation either in person or via video conference.

Each study volunteer who agrees to participate in the study will be asked to complete an Informed Consent Form (Appendix 6). A parent or guardian will need to consent for subjects under 18 years old. Study subjects between the ages of 7 and 17 years old will be asked to complete an Assent form (Appendix 7). Specimens will be collected and tested only after the Informed Consent form is completed. Each study volunteer will be assigned a unique specimen identification number (SID). The Clinical Investigators or designees will observe AN swab collection and testing. Subjects will collect AN swab samples and perform the Rapid SARS-CoV-2 Antigen Test using only the IFU for instruction or video linked from the IFU. The collection devices and storage tubes will be appropriately labeled with the SIDs and not the names of the participants to maintain confidentiality.

Rapid SARS-CoV-2 Antigen Test AN swab specimens will be collected and tested per the product directions that accompany the device (Appendix 1). Following Rapid SARS-CoV-2 Antigen Test, subjects will complete a System Usability Scale questionnaire (Appendix 4) and an Ease of Use assessment including interpretation of mock test cassettes (Appendix 5).

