#### **4.4 Sample Types and Numbers**

Subjects will be enrolled in an “all comers” style, including both symptomatic and asymptomatic patients. The study population will include subjects from 2 years old to greater than 65 years old. Minors must be consented by their parent or legal guardian. The parent or legal guardian should collect the samples and perform testing if the child is between 2 and 13 years old. Older children ages 14-17 should collect their samples and perform their tests without their parent or legal guardian intervening. The study will include two sections, 50 subjects testing themselves and 50 subjects testing another person such as children between the ages of 2 and 13 years old. Enrollment efforts in various zip codes will be pursued in order to represent different socioeconomic and educational backgrounds and this information will be captured in the tester questionnaire (Appendix 2) and subject questionnaire (Appendix 3). A portion of the study population should include Spanish speaking users. High risk individuals will not be excluded. Participants who regularly use home diagnostic tests, such as glucose meters, will be excluded. Study testing will continue until the full range of 2-65+ ages are tested including at least 50 self-tests and 50 tests performed by subjects on other participants.

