### 6.2.2 Exclusion of Data from Analysis

Data from invalid runs results will be excluded. All excluded results will be documented with rationale for exclusion and a summary of these cases will be provided.

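### The SUS is scheduled only after the test or its interpretation, with no provision for testers who stop part-way, so the 68-point mean may rest on successful users

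*Protocol*

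**What the plan says.** Protocol section 4.0 sets two acceptance criteria. One concerns the control line: "The study acceptance criteria is a 95% success rate for subjects producing the control line on the Rapid SARS-CoV-2 Antigen Test". The other is "a SUS average score of 68 or greater". The testers over whom the SUS is averaged are not named.

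The protocol gives two time points for the SUS. Section 4.0 describes the full sequence of steps, "The study subjects shall perform the entire workflow including sample collection, testing, and results interpretation", and then continues: "Following results interpretation, subjects will complete a usability and ease of use questionnaires". Section 4.3 ties the questionnaire to the test itself: "Following Rapid SARS-CoV-2 Antigen Test, subjects will complete a System Usability Scale questionnaire (Appendix 4". That sentence goes on to the Ease of Use assessment with its mock cassettes.

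Three other places bear on who ends up with a score:

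- Section 4.4 continues testing until all ages are covered, "including at least 50 self-tests and 50 tests performed by subjects on other participants".
- Section 6.2.5 has invalid results repeated, by the same or another subject, until the section 4.4 numbers are met.
- Sections 6.2.1 and 6.2.2 limit the final analysis to valid results from valid runs. Section 6.2.2 opens with "Data from invalid runs results will be excluded" and asks for the exclusions to be documented and summarised.

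Section 3.3 foresees incomplete runs but gives no questionnaire rule for them.

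**The concern.** A tester who cannot follow the instructions and stops during swabbing, extraction or loading reaches neither of the two points at which the SUS is scheduled. Nothing in the protocol tells the observer to hand over the form anyway. If testing then goes on with someone else until the target count is reached, the SUS set fills up with people who got through the procedure. A tester whose first card is invalid and who repeats the test may give a score that reflects practice, because the protocol does not say which attempt the SUS follows.

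Section 2.2 names the clarity and robustness of the instructions as the main focus. Testers for whom the instructions failed are the most informative on that question and would be expected to give the lowest ratings. Losing them pushes the mean upwards, towards acceptance, on one of only two acceptance criteria. Section 9.0 says that the results will be used to show suitability for home use, and section 4.0 that they may go into a regulatory filing.

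**Working it through.** There is no stated figure to reproduce. The threshold of 68 and the 50 + 50 tests are fixed without a derivation, and the protocol gives no abandonment rate, SUS standard deviation or expected mean. What follows is a sensitivity calculation. From section 4.0 it takes only the 68 and the 95%, and from section 4.4 the 100 tests (50 + 50). Everything else is an assumption.

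**1. Shift of the mean.** Let f be the share of testers without a score, M the mean SUS of those with one and S the mean SUS the others would have given. The mean over all testers is (1 − f)M + fS, so the collected mean is too high by f(M − S). With f = 5% and an assumed gap M − S of 20, 30 or 40 points:

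- 0.05 × 20 = 1.0
- 0.05 × 30 = 1.5
- 0.05 × 40 = 2.0

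**2. Share that turns a pass into a fail.** Setting (1 − f)M + fS = 68 gives f = (M − 68)/(M − S). With S assumed between 0 and 50:

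| M | f at S = 0 | f at S = 50 |
|---|---|---|
| 70 | 2/70 = 2.9% | 2/20 = 10.0% |
| 75 | 7/75 = 9.3% | 7/25 = 28.0% |
| 80 | 12/80 = 15.0% | 12/30 = 40.0% |

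The omission decides the outcome only when the collected mean is close to 68 or stopping is frequent.

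**3. The limit set by the control-line criterion.** If everyone who starts is in the control-line denominator, at most 5 of 100 may fail to produce a line; with more, the study fails whatever the SUS. With 5 of 100 missing from the SUS, the other 95 need a mean of (6800 − 5S)/95 for the all-tester mean to reach 68:

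- S = 0: 6800/95 = 71.58
- S = 25: 6675/95 = 70.26
- S = 40: 6600/95 = 69.47
- S = 50: 6550/95 = 68.95

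At the threshold the overstatement is then about 1.0 to 2.3 points for S from 50 to 25, and 3.6 points in the extreme case of S = 0.

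**4. Without that limit.** If testers who stop are excluded or replaced, and so leave the control-line denominator too, larger shares become possible. With 90 testers averaging 70 and 10 who would have averaged 40, the collected mean is 70 (pass) and the all-tester mean is 0.9 × 70 + 0.1 × 40 = 67.0 (fail). If those 10 counted as control-line failures, the rate would be at most 90% and the study would fail on that criterion.

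**5. Effect on the chance of passing.** Assume an SD of 20 and 100 scores, so SE = 20/√100 = 2. With an all-tester mean of 67, the chance that the observed mean reaches 68 is 1 − Φ(0.5) = 0.31. A 1-point shift makes it 0.50, and a 2-point shift makes it Φ(0.5) = 0.69.

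**The case against.** The strongest objection is that this reads a rule into silence. A reader might infer that testers who give up never enter the SUS mean and that the criterion is computed on completers. The protocol does not say so. Section 4.0 describes the normal order of steps and does not make a result a condition for the form, and an observer attends every test and could hand it over. That stands, so the point is what may happen if the text is followed as written.

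A reader might also infer that a tester with an invalid card loses the SUS. That is not supported: under section 4.3 such a tester has finished the test and can complete the form. Only those who stop earlier are plausibly missed. For an invalid card the open question is which attempt the score follows.

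Nor do sections 6.2.1 and 6.2.2 clearly remove SUS scores. They speak of specimens, remaining volume and results, do not mention questionnaires, and require exclusions to be reported. The opening of 6.2.2 is broad enough to be read as covering all data from an invalid run, but that is the less natural reading.

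Replacement of a tester who stops is likewise not written down. Section 4.4 also counts in subjects, its totals are minimums, and 6.2.5 covers invalid results, not abandonment. What stands is that testing continues until the number of tests is reached, which an abandoned test does not obviously count towards.

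Finally, the averaging set and the handling of missing scores can be left to a statistical analysis plan, and testing procedures that are not shown may address early stopping. The first part is right as far as analysis goes. But who is given the questionnaire, and when, is data collection that this protocol fixes; no analysis plan can recover a form that was never completed.

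**Conclusion.** The point holds as a gap in data collection, not as a stated exclusion. Followed as written, the protocol can leave the 68-point mean resting on testers who used the kit successfully, or on scores given after a repeat. Either would favour acceptance.

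The size cannot be determined from the protocol. With 5% of testers missing and an assumed gap of 20 to 40 points, the overstatement is 1 to 2 points. That is enough to matter near 68 and unimportant if the mean is well above it: at a collected mean of 80, 15% to 40% would have to be missing to reverse a pass. Shares of 10% or more affect the decision only if those testers also drop out of the control-line denominator, which section 4.0 does not define. All of this assumes that testers who stop would score lower, which is plausible but not documented. The change is worth making because it is cheap and removes a bias in one direction.

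**What to change.** - In sections 4.0 and 4.3, state that every tester who opens a kit completes the SUS and the mock-cassette reading once, at the end of the first attempt, whether the test was completed, invalid or abandoned.
- In section 6.2.2, state that the exclusion covers card results only, so that SUS and Ease of Use data are kept.
- In section 4.0, state that the 68-point criterion is computed on all testers who opened a kit.

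The cost is a change of wording. The observer is already present and the forms already exist. The downside is a possibly lower mean SUS and a few minutes with testers who stopped.

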### 4.1 Site Characteristics

EDP Biotech Corp. is currently offering specimen collection for patient SARS-CoV-2 testing in a clinic setting. For referral and internet recruiting and specimen collection, EDP personnel will observe specimen collection and testing from patients in their homes or by remote visual monitoring via video conference after consenting. The site has a CLIA certificate (44D2184836) and has the requisite infrastructure to perform molecular testing. EDP Biotech Corp. is currently offering SARS-CoV-19 testing to patients. All personnel involved in the study will be qualified by education and experience to conduct this study and agree to follow the study protocol.

### 4.2 Site Personnel

EDP Biotech Corp. management of the laboratory involved in this evaluation is responsible for assignment of qualified personnel and for maintaining documented required qualifications for those personnel.

### 4.3 Specimen Collection

Each potential subject will be asked to complete a form describing any symptoms of respiratory illness being experienced, education level, and basic demographics (Appendices 2 and 3). Subjects will be observed by EDP Biotech Corp. personnel or

designees during sample collection, testing, and shipment preparation either in person or via video conference.

Each study volunteer who agrees to participate in the study will be asked to complete an Informed Consent Form (Appendix 6). A parent or guardian will need to consent for subjects under 18 years old. Study subjects between the ages of 7 and 17 years old will be asked to complete an Assent form (Appendix 7). Specimens will be collected and tested only after the Informed Consent form is completed. Each study volunteer will be assigned a unique specimen identification number (SID). The Clinical Investigators or designees will observe AN swab collection and testing. Subjects will collect AN swab samples and perform the Rapid SARS-CoV-2 Antigen Test using only the IFU for instruction or video linked from the IFU. The collection devices and storage tubes will be appropriately labeled with the SIDs and not the names of the participants to maintain confidentiality.

Rapid SARS-CoV-2 Antigen Test AN swab specimens will be collected and tested per the product directions that accompany the device (Appendix 1). Following Rapid SARS-CoV-2 Antigen Test, subjects will complete a System Usability Scale questionnaire (Appendix 4) and an Ease of Use assessment including interpretation of mock test cassettes (Appendix 5).

#### **4.4 Sample Types and Numbers**

Subjects will be enrolled in an “all comers” style, including both symptomatic and asymptomatic patients. The study population will include subjects from 2 years old to greater than 65 years old. Minors must be consented by their parent or legal guardian. The parent or legal guardian should collect the samples and perform testing if the child is between 2 and 13 years old. Older children ages 14-17 should collect their samples and perform their tests without their parent or legal guardian intervening. The study will include two sections, 50 subjects testing themselves and 50 subjects testing another person such as children between the ages of 2 and 13 years old. Enrollment efforts in various zip codes will be pursued in order to represent different socioeconomic and educational backgrounds and this information will be captured in the tester questionnaire (Appendix 2) and subject questionnaire (Appendix 3). A portion of the study population should include Spanish speaking users. High risk individuals will not be excluded. Participants who regularly use home diagnostic tests, such as glucose meters, will be excluded. Study testing will continue until the full range of 2-65+ ages are tested including at least 50 self-tests and 50 tests performed by subjects on other participants.

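### Section 4.4 does not exclude testers who have already used, watched or been swabbed with this kit, so they count in full toward criteria meant to judge the instructions

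*Protocol*

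**What the plan says.** Section 2.2 makes the instructions for use the main thing under test. Section 4.3 accordingly has subjects perform the test "using only the IFU for instruction or video linked from the IFU", and section 4.0 sets two acceptance criteria: 95% of subjects producing the control line, and a mean SUS score of at least 68.

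Eligibility and numbers are in section 4.4:

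- Enrolment is open: "Subjects will be enrolled in an “all comers” style, including both symptomatic and asymptomatic patients".
- The only exclusion based on experience is "Participants who regularly use home diagnostic tests, such as glucose meters, will be excluded".
- The two sections are "50 subjects testing themselves and 50 subjects testing another person such as children" aged 2 to 13. Nothing says that the two sets of testers, or their households, must be distinct.
- Testing goes on until the age range is covered, "including at least 50 self-tests and 50 tests performed by subjects on other participants". This counts tests, not people who are new to the kit.
- For young children, "The parent or legal guardian should collect the samples and perform testing if the child is between 2 and 13 years old". Those aged 14 to 17 test themselves without a parent intervening.

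Recruitment is "through the internet as well as by referral throughout the United States" (section 4.0), and testing is observed in homes or by video (section 4.1). Section 6.2.5 lets the same subject repeat an invalid test.

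**The concern.** A usability study of written instructions needs testers who meet the procedure through those instructions. By excluding regular users of home tests, the protocol accepts that experience matters. That exclusion misses the closest form of experience, which is contact with this very kit.

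The text leaves several routes open. A parent may self-test and then test a child. One adult may watch another test at home and then take a turn. A person aged 14 or over who was swabbed by someone else may go on to self-test. A subject may repeat an invalid test. In each case the later test can count toward the 50 + 50 and both criteria.

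Earlier sight of the steps would more plausibly help than hinder, so any bias would tend toward passing. If exposure is not recorded, no later analysis can separate the exposed testers from the rest.

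**Working it through.** **Do the existing safeguards cover earlier exposure?**

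| Provision | What it controls | Covers earlier exposure to this kit? |
|---|---|---|
| 4.3, IFU or linked video only | Source of instruction for the attempt | No |
| 4.0, 4.1, 4.3, 5.6, observer present | Conduct of the attempt | No |
| 4.4, no parental intervention at ages 14-17 | Help during the attempt | No |
| 4.4, regular users of home tests excluded | Habitual experience with other tests | No |
| 7.2, tester form (race and ethnicity, zip code, language) | Background data | Not listed; the form is not shown, and no exclusion in the text depends on it |

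**What could it do to the control-line criterion?** The protocol gives no expected success rate and no derivation of 50 + 50, so there is no figure to reproduce. What follows is illustration only.

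*Inputs.* From the protocol: 100 tests and the 95% criterion, read here as at least 95 successes among the pooled 100. Assumed: success p among unexposed testers, success q among exposed testers, and the exposed share f.

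*Pooled rate* = (1 − f)·p + f·q. With p = 92% and q = 98% this is 92 + 6f:

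- f = 0.30: 0.7 × 92 + 0.3 × 98 = 64.4 + 29.4 = 93.8%
- f = 0.50: 0.5 × 92 + 0.5 × 98 = 46 + 49 = 95.0%
- Setting 92 + 6f = 95 gives f = 3/6 = 0.50, so a smaller share leaves the expected rate below 95%.

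*Chance of passing* = P(X + Y ≥ 95), with X ~ Binomial(100 − k, p) for unexposed testers and Y ~ Binomial(k, q) for the k exposed testers, taken as independent. With q = 98%:

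| Unexposed success p | k = 0 | k = 10 | k = 25 | k = 50 |
|---|---|---|---|---|
| 88% | 0.015 | 0.030 | 0.076 | 0.286 |
| 90% | 0.058 | 0.092 | 0.178 | 0.438 |
| 92% | 0.180 | 0.242 | 0.360 | 0.616 |

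With q = 99% the k = 50 column becomes 0.356, 0.525 and 0.706.

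Ten exposed testers change little. Twenty-five at least double the chance that instructions falling short of 95% are accepted (0.360/0.180 = 2.0 at p = 92%). Fifty is an upper-end case: with two testers per household and only the second exposed, all 50 households would have to supply two testers, and every second tester would have to have been exposed.

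No comparable calculation is possible for the SUS average, because the protocol gives neither a spread nor an expected effect.

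**The case against.** A reader might infer that the second tester in a home learns from the first instead of from the IFU. The protocol does not support that. Section 4.3 restricts instruction to the IFU and its video, every attempt is observed, and section 6.2 requires deviations to be reported. Coaching by a relative would be a visible breach. What is left is earlier exposure, whose effect would come on top of the IFU.

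A reader might also infer that the study recruits household pairs. It does not say so. Recruitment is by internet and referral (4.0), with public posting and e-mail added in section 9.0, and across various zip codes. Parent and child pairs arise naturally only in the section where one person tests another. Shared households across the two sections are possible but not planned.

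Nor can just anyone who was swabbed move on to self-testing. Children aged 2 to 13 are to be tested by a parent or guardian, which closes that route for the section's own example. It stays open only for people aged 14 or over, in unknown number.

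The assumed 92% and 98% have no source in the protocol. The contrast may be smaller, since an IFU-only tester may already watch the linked video. The forms in Appendices 2, 3 and 5 are not shown and might ask about earlier contact with the kit.

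All of this limits the likely size. None of it closes the gap: no stated rule stops an exposed tester from being counted.

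**Conclusion.** The gap is real and belongs in the protocol, because it concerns who is eligible and who is counted. Section 4.4 allows testers with earlier exposure to this kit to count in full toward criteria meant to assess the instructions. The likely direction is toward passing, for both the control-line rate and the SUS average. That direction is a judgement, not something the protocol states.

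The size is unknown. Under the assumed 92% and 98%, 30% exposure still leaves the expected rate at 93.8%, short of the criterion. It would therefore go too far to say that the study will pass on exposure alone, or that exposure will occur. This is an inexpensive improvement worth making before enrolment, not a defect that invalidates the design.

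**What to change.** Add to section 4.4 that a tester counts toward the 50 + 50 and the acceptance criteria only if, before their own attempt, they have not used this kit, watched it being used or been swabbed with it. Ask this at screening and record the answer.

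Where two testers share a household, have the second wait out of sight of the first test, with the observer confirming and recording this. Otherwise record the second test but do not count it. Word this as a rule on counting rather than on eligibility, so that an exposed person may still take part without contradiction.

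Section 6.2.5 should be aligned: under this rule a same-subject repeat is recorded but does not count as the test of a new user.

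The cost is one sentence on counting, one screening question and one observer entry. Enrolment will be slightly slower in homes with several testers. Over video, the out-of-sight confirmation rests partly on self-report.
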